Glottic view using supraglottic devices in pediatric patients

NCT02532465

IRB Approval Date: 8/7/2015

Glottic view using supraglottic devices in pediatric patients

PI: [name]

Co-investigators: [name], [name], [name]

Describe the background and rationale for this project. Reference to peer reviewed literature is desirable: Endotracheal intubation is the gold standard for securing the airway. However, while managing patients with difficult airways, various supraglottic devices have been used as rescue airway devices. Laryngeal mask airways (LMAs) are among the most commonly used supraglottic devices. After placement, subsequent intubation with an endotracheal tube via the LMA is achieved either blindly or with the use of a fiberoptic device. Several modifications of the LMA have been developed since its introduction in 1983 to improve their ease of initial use, multimodal function, and subsequent facilitation of ETT placement. Modifications of the classic LMA have included the intubating LMA (I-LMA) and variants (LMA Fastrach, Air-Q and LMA-Supreme).

Another supraglottic device and variant of the LMA is known as the i-gel. The i-gel does not have an inflatable cuff. In the i-gel, the traditional cuff of the LMA is replaced with a soft, gel-like, and transparent thermoplastic elastomer (styrene ethylene butadiene styrene) which is a mirror impression of the supraglottic/periglottic anatomy and creates a non-inflatable seal.¹ The unique features of i-gel also include a separate conduit for gastric suction, an epiglottic ridge, and a ridged flattened stem to aid insertion and reduce the risk of axial rotation, a rigid stem and a bite block.^{2,3} The i-gel® has also been used in rescue airway management and as a conduit for tracheal intubation.³⁻¹⁰

Recently, there have been attempts to compare the various LMAs and the ease of subsequent intubation through the different types of LMAs in adult patients.¹¹⁻¹² The aim of our current study is to compare the fiberoptic view through the internal aspect of the i-gel versus the Air-Q LMA in pediatric patients. By examining the fiberoptic view through these two devices, we will determine which device provides a clearer passage to the glottic opening and is therefore the preferred conduit to aid endotracheal intubation in difficult airways.

Describe the significance of the proposed research:

Although management of the difficult airway is generally rare in the pediatric population, it is one of the leading causes of perioperative morbidity and mortality. Simple and effective techniques to secure the difficult airway are needed. This study would help define the optimal supraglottic device for that purpose.

State the primary and secondary objectives of the study: We will compare the fiberoptic view of the glottic aperture by passing a fiberoptic

bronchoscope through two types of supraglottic airways (the Air-Q LMA or the i-gel LMA).

If this research is hypothesis driven, succinctly state the hypothesis:

The i-gel LMA will provide a better bronchoscopic view of the glottic aperture than the Air-Q LMA.

Outline the major steps and methodologies in the clinical protocol(s).

If necessary, include a description of any procedures being performed already for diagnostic or treatment purposes: General anesthesia with the use of an LMA or supraglottic device is routinely performed on more than half of the pediatric patients undergoing general anesthesia every day in our operating rooms. There will be no change in the anesthetic care during these procedures; however, 100 patients would be randomized to one of two types of supraglottic devices; i-gel or LMA (Air-Q). Following placement of the supraglottic device, a fiberoptic bronchoscope will be inserted through the LMA to its distal end and a picture of the glottis aperture will be obtained. The following scoring system will be used^{13,14}:

1. vocal cords not seen, but ventilation adequate
2. vocal cords + anterior epiglottis
3. vocal cords + posterior epiglottis
4. only vocal cords seen

Placement of the fiberoptic bronchoscope will be performed after the administration of general anesthesia and 100% oxygen to avoid any risk of oxygen desaturation. The procedure will take less than 15 seconds and the bronchoscope will not exit the distal end of the supraglottic device. Therefore, it will not touch the airway. Given this, there is no additional risk although the use of the fiberoptic bronchoscope for the purpose of the study only.

Identify the variables to be measured and how they will be statistically evaluated: A Fishers' exact test and a contingency table will be used to compare the bronchoscopic view through the two different supraglottic devices. Most importantly, the percentage of acceptable/good view (grade 3 or 4) will be compared to poor view (grade 1).

References:

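### One pooled Fisher test with no size-stratified analysis: valid, but inefficient if child size predicts the fiberoptic view

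*Combined protocol and SAP*

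**What the plan says.** The document is a short combined protocol. Its aim, at the end of the background section, is to "compare the fiberoptic view through the internal aspect of the i-gel versus the Air-Q LMA in pediatric patients". That phrase is the only description of the population, and no age, weight or device-size limits are given.

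The section outlining the clinical protocol says "100 patients would be randomized to one of two types of supraglottic devices; i-gel or LMA (Air-Q"). It does not state the allocation ratio, blocking, stratification factor or randomisation method.

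The section on variables and their statistical evaluation gives one method: "A Fishers' exact test and a contingency table will be used to compare the bronchoscopic view through the two different supraglottic devices". It then names the contrast of most interest: "Most importantly, the percentage of acceptable/good view (grade 3 or 4) will be compared to poor view (grade 1"). Grade 2 belongs to neither side of that contrast. No covariate, stratum or subgroup is named.

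The hypothesis is directional: "The i-gel LMA will provide a better bronchoscopic view of the glottic aperture than the Air-Q LMA". No significance level, power, expected rate or basis for 100 patients is stated.

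**The concern.** The outcome is anatomical: what can be seen of the cords and epiglottis from the distal end of the device. In a population described only as pediatric, body size is a natural candidate for a factor that affects that view. Weight can be recorded before randomisation.

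If size does matter, two things follow.

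- The pooled table treats the size-related spread in grades as noise, so the test has less power than one that compares the devices among children of similar size.
- The two arms can differ in size mix by chance, and a pooled table can neither show this nor allow for it.

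The protocol intends to name a preferred conduit from about 50 children per arm, so avoidable loss of precision is worth removing when this needs no more patients.

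**Working it through.** **Plan's own figure.** The total of 100 cannot be reproduced, because no rates, effect size, significance level or power are given. Everything below is therefore illustrative.

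**Inputs.** From the document: 100 patients, two devices, Fisher's exact test. Assumed: 1:1 allocation (50 per arm), two-sided 5% level, a binary good-view outcome in all 100 children, a common odds ratio of 3 in favour of the i-gel, and the Air-Q good-view rates by size shown in the table.

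**1. Chance imbalance.** Suppose 50 of the 100 children are small. The number of small children in one arm is hypergeometric, with variance 50 × 0.5 × 0.5 × 50/99 = 6.31 and SD 2.51. If one arm has x small children, the other has 50 − x, so the shares differ by (2x − 50)/50. The SD of that difference is 2 × 2.51/50 = 0.10, or 10 points.

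- P(difference of 10 points or more) = 0.317. The difference moves in steps of 4 points, so this means 12 or more.
- P(difference of 20 points or more) = 0.071.

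Shift in the observed device difference = imbalance × gap in good-view rate between sizes:

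- 40-point gap: 0.10 × 0.40 = 4 points; 0.20 × 0.40 = 8 points.
- 20-point gap: 2 and 4 points.

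For scale, at a rate of 60% the SD of the device difference is √(2 × 0.6 × 0.4/50) = 0.098, about 10 points.

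**2. Why pooling can lose power.** Take Air-Q rates of 40% and 80% in equal halves.

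- Overall rate 60%, total variance 0.6 × 0.4 = 0.24.
- Variance within size groups: 0.5 × (0.4 × 0.6) + 0.5 × (0.8 × 0.2) = 0.20. So 0.04/0.24 = 17% of the variance comes from size.
- At 50%/70%, the within-group variance is 0.5 × 0.25 + 0.5 × 0.21 = 0.23, and the share from size is 0.01/0.24 = 4%.

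Pooling also shrinks the odds ratio. An odds ratio of 3 takes 40% to 66.7% and 80% to 92.3%, mean 79.5%. The pooled odds ratio is (0.795/0.205)/(0.6/0.4) = 2.6.

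**3. Simulated power** (5,000 to 8,000 trials per scenario in separate runs, error about ±1 point). The stratified exact test conditions on the margins within each size group and combines the groups.

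| Air-Q rates, small/large | Split | Pooled Fisher | Stratified exact |
|---|---|---|---|
| 40%/80% | 50:50 | 48–50% | about 57% |
| 30%/85% | 40:60 | 36% | 48% |
| 50%/70% | 50:50 | 59% | 61–63% |
| 60%/60% | 50:50 | 60–61% | 62–63% |

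Type I error was about 3% for pooled Fisher and at most about 4% for the stratified exact test. The mean device difference under the null was about zero.

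**4. Is the gain just Fisher's conservatism?** Comparing pooled chi-square with the Cochran-Mantel-Haenszel (CMH) test removes that explanation: 57.9% to 64.6% at 40%/80%, and 43.8% to 55.7% at 30%/85%. A second setting used three equal size groups and an odds ratio of 3.5. It gave 78% to 77% with no size effect, 74% to 76% with a moderate one (45/60/75%) and 64% to 73% with a strong one (30/60/85%).

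**5. Does blocked allocation add power?** No. In one set of runs the stratified exact test had 58.5% power with unstratified allocation and 57.2% with allocation balanced within size groups (40%/80%), and 48.7% against 48.2% (30%/85%). A separate set gave 57.9% against 54.4% and 47.0% against 44.3%.

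**The case against.** A reader might infer that children of every size enter a single unstratified pool. The document does not say so. It is silent on the size range and on the randomisation method, and silence in a brief protocol may be a reporting gap rather than a design choice. That objection stands. What can be said is that no size factor is stated for allocation or analysis.

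A reader might also infer that power is certainly lost. Nothing in the document says that size affects the view. The larger gains need good-view rates 40 or 55 points apart by size. At a 20-point gap the gain is about 2–4 points, and with no size effect it is close to simulation error. This stands too, so the point is conditional.

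The imbalance argument must not be read as bias. Randomisation keeps the test valid, and a one-SD imbalance with a 20- to 40-point size effect moves the estimate by 2–4 points, well inside its SD of about 9–10.

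Finally, the simulations use a binary outcome in all 100 children, whereas the plan's main contrast omits grade 2. Fewer than 100 children may enter it, so the absolute power figures may not carry over.

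None of this gives a reason to prefer the pooled test. In none of the scenarios did the stratified exact test do worse than pooled Fisher by more than simulation error.

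**Conclusion.** The point holds in conditional form. The planned test is valid. If child size predicts the view, it is less efficient than a size-stratified exact test on the same children. Under the assumptions above, the gain is about 7–12 points of power for a strong size effect, 2–4 for a modest one and 1–2 for none. The strong-effect figure is somewhat smaller in some runs with blocked allocation.

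The document does not support a claim that the result would be biased, that the type I error is inflated, or that stratified randomisation is needed to recover power. The case for change rests on low cost, not on a demonstrated size effect.

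**What to change.** In the clinical-protocol outline, state the eligible age or weight range and the randomisation method, and add that weight is recorded before randomisation and that two or three weight bands are fixed before enrolment.

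In the statistical section, replace the pooled Fisher test as the main comparison with wording such as:

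> *The devices will be compared on good view (grade 3 or 4) with an exact test stratified by weight band (Cochran-Mantel-Haenszel type). The handling of grade 2 in this contrast is prespecified as [state]. The table of grades by device will also be shown within each band.*

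Use weight rather than device size to define the bands, since the two devices' sizes need not correspond. Blocked allocation within bands is optional: it guards against visible imbalance but does not add power. If the allocation list is already fixed, the stratified test alone is enough.

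The cost is one baseline value per child, bands chosen in advance and a few sentences of text. No extra patients or procedures are needed. The drawback is that the bands must be set before enrolment, and the gain is negligible if size proves unrelated to view.

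### The view is graded on an ordered 1–4 scale and the hypothesis is that i-gel is better, but no planned comparison uses the full order, and the emphasised one leaves grade 2 out

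*Combined protocol and SAP*

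**What the plan says.** The hypothesis section is directional: "The i-gel LMA will provide a better bronchoscopic view of the glottic aperture than the Air-Q LMA". The background section gives the aim in the same terms: "we will determine which device provides a clearer passage to the glottic opening".

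The methodology section scores the bronchoscopic picture in four grades. Grade 1 is "vocal cords not seen, but ventilation adequate" and grade 4 is "only vocal cords seen". On sample size it says only that "100 patients would be randomized to one of two types of supraglottic devices".

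The section on variables and their statistical evaluation has two sentences. The first is "A Fishers' exact test and a contingency table will be used to compare the bronchoscopic view through the two different supraglottic devices". The second is "Most importantly, the percentage of acceptable/good view (grade 3 or 4) will be compared to poor view (grade 1". The labels in that second sentence (3 or 4 acceptable or good, 1 poor) show that the plan itself treats the scale as ordered.

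The document names no rank, trend or other ordinal method. It gives no significance level, sidedness, allocation ratio, expected grades, effect size or power.

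**The concern.** The question is one of order (which device gives the clearer view), and the outcome is recorded on an ordered scale. The two planned comparisons do not match that.

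- **Fisher's test on the device-by-grade table** treats the four grades as unordered labels. Its p-value is the same if the grade columns are shuffled. It can be small because one device is merely more variable, and a small p-value does not say which device is better.
- **Grades 3–4 against grade 1** has a direction, but it counts 3 and 4 as the same result, so it cannot register a move to the clearest view on the scale. It also gives grade 2 no place. A child who scores 2 leaves the comparison because of the outcome, so the groups compared are no longer the groups randomised.

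At stake is whether the trial can support its own conclusion about the preferred device, and how much of the information from 100 children it uses.

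**Working it through.** **The plan's own figure.** The only figure is 100 patients. It cannot be reproduced, because no level, power, rates or effect size are given.

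**Inputs.** From the documents: total 100, four ordered grades, Fisher's exact test, grades 3–4 against grade 1. Assumed here: 50 per arm, two-sided 0.05, and all grade distributions. Tables list counts at grades 1/2/3/4. The Fisher p-value for four grades comes from full enumeration with fixed margins; the rank-sum p-value is tie-corrected.

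**1. A difference with no better device.** Take i-gel 15/10/10/15 and Air-Q 5/20/20/5.

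- Mean grade: (15 + 20 + 30 + 60)/50 = 2.5 for i-gel; (5 + 40 + 60 + 20)/50 = 2.5 for Air-Q.
- Probability that an i-gel child has the higher grade, ties counted half: pairs with i-gel higher = 10×5 + 10×25 + 15×45 = 975; ties = 15×5 + 10×20 + 10×20 + 15×5 = 550; (975 + 275)/2500 = 0.50.
- Fisher on four grades: p = 0.0008. Rank-sum: p = 1.00.
- Grades 3–4 of all children: 25/50 in each arm. With grade 2 removed: 25/40 = 62.5% against 25/30 = 83.3%, Fisher p = 0.067. The apparent gap comes only from removing grade 2.

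In simulated trials with the same proportions (30/20/20/30% against 10/40/40/10%), Fisher on four grades rejects in 95%, grades 3–4 against 1 in 42%, and rank-sum in 5%.

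**2. A shift across the whole scale.** Take i-gel 4/8/15/23 and Air-Q 8/13/16/13. Mean grades are 157/50 = 3.14 and 134/50 = 2.68. Fisher on four grades gives p = 0.153; grades 3–4 against 1 (38/42 against 29/37) gives p = 0.209; rank-sum gives p = 0.022.

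**3. Power for such shifts.** A common odds ratio of 3 means that, at each cut k, odds(grade ≤ k) for i-gel = odds(grade ≤ k) for Air-Q ÷ 3. For Air-Q 10/20/30/40% the cumulative odds are 0.111, 0.429 and 1.5. Divided by 3 they are 0.037, 0.143 and 0.5, which gives i-gel about 4/9/21/67%. Power from about 2,000 simulated trials per row:

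| Air-Q grades 1–4 | i-gel grades 1–4 | Fisher, four grades | Fisher, 3–4 v 1 | Rank-sum |
|---|---|---|---|---|
| 10/20/30/40% | 4/9/21/67% | 65% | 27% | 82% |
| 5/10/35/50% | 2/4/19/75% | 62% | 7% | 76% |
| 25/25/25/25% | 10/15/25/50% | 71% | 61% | 85% |

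The simulation standard error is at most √(0.25/2000) = 1.1 points. Allowing for it, the ranges are about 61–73%, 7–61% and 76–87%. With no difference between devices, Fisher on four grades and rank-sum each reject in about 5%.

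**4. Children lost with grade 2.** In the same rows, the expected numbers removed are 50×(0.20 + 0.09) = 14.5, 50×(0.10 + 0.04) = 7 and 50×(0.25 + 0.15) = 20 of 100.

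**5. A move between grades 3 and 4 only.** Take i-gel 5/10/10/25 and Air-Q 5/10/25/10. Grades 3–4 against 1 compares 35/40 with 35/40, so p = 1.00. Fisher on four grades gives p = 0.004 and rank-sum p = 0.057. With proportions 10/20/20/50% against 10/20/50/20%, power is about 89% for Fisher on four grades and 49% for rank-sum.

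**The case against.** - **The plan does not say that the table has four columns.** This stands. Fisher's test may be meant only for the good-against-poor contrast. The first sentence compares the view as a whole and the second then singles out part of it, so four grades is the natural reading, but not a certain one. On the narrower reading, the argument about order-blindness falls away. What remains is the pooling of 3 with 4 and the loss of grade 2, with the lower power figures.
- **Fisher's test is valid.** This stands. A reader might infer an inflated false-positive rate; with identical grade distributions the test rejects in about 5%, so there is none. The limit is on what a rejection means.
- **The investigator would see the direction from the table and the percentages.** Partly true. The plan nowhere says that a significant four-grade result alone would be read as i-gel being better. But it gives no rule linking the test to the directional claim, and the emphasised percentages can mislead once grade 2 is removed. The example with no better device is deliberately extreme, and nothing in the documents suggests that either device behaves that way.
- **The power gain depends on the scenarios.** This stands. All three rows are proportional-odds shifts, which suit a rank test. For a move only between grades 3 and 4 the ranking reverses. So the documents do not support the tempting claims that the rank-sum test is always better, or that Fisher on four grades would miss a 3-to-4 move. Only the pooled comparison is blind to that move.

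**Conclusion.** The point holds in a limited form. The plan states a directional hypothesis on an ordered scale, and neither planned comparison uses the whole order. If Fisher's test is applied to all four grades, significance shows a difference in distribution rather than a better view. Whichever table Fisher's test is meant for, the comparison given most weight cannot see a move from grade 3 to grade 4 and excludes randomised children by outcome.

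For shifts across the whole scale at an odds ratio of 3, the rank-sum test gains about 14 to 17 points of power over Fisher on four grades (76 − 62, 85 − 71 and 82 − 65). Its gain over grades 3–4 against 1 is 24 to 69 points (85 − 61 and 76 − 7). These sizes rest on the assumed 50 per arm, two-sided 0.05, the three assumed Air-Q distributions and the proportional-odds form; none of these is in the documents. The mismatch between hypothesis and analysis, and the absence of grade 2 from the emphasised comparison, do not depend on those assumptions.

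**What to change.** Replace the two analysis sentences with text to this effect:

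*The primary analysis compares the 1–4 grade between devices as an ordered outcome, by a two-sided Wilcoxon rank-sum test (tie-corrected or exact). The result is reported as the probability that a child with i-gel has a higher grade than a child with Air-Q, ties counted half, with a 95% confidence interval. I-gel will be called better only if this comparison favours i-gel. The device-by-grade table is descriptive. The supporting summary is the percentage of all randomised children in each arm with grade 3 or 4, with grade 2 counted in the denominator.*

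State the significance level in the same place, since the plan gives none.

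The cost is a few sentences, with no new patients, data or procedures. There is a downside to accept knowingly: the ordinal test has less power than Fisher on four grades when the devices differ only in spread, or only by a move between grades 3 and 4 (about 49% against 89% in the scenario above). Keeping the full table as description leaves such patterns visible.

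### The comparison ranked first sets grades 3-4 against grade 1 and leaves grade 2 without a category, so it need not estimate the good-view rate among randomised patients

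*Combined protocol and SAP*

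**What the plan says.** The protocol's section on major steps and methodologies defines four grades of view. Grade 1 is "vocal cords not seen, but ventilation adequate", grade 2 is "vocal cords + anterior epiglottis", and in grades 3 and 4 the cords are seen with the posterior epiglottis or alone. The number of patients is given in the same section: "100 patients would be randomized to one of two types of supraglottic devices". No allocation ratio is stated.

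The section on variables and their statistical evaluation has two sentences. The first is general: "A Fishers' exact test and a contingency table will be used to compare the bronchoscopic view through the two different supraglottic devices". It neither restricts the grades nor gives the dimensions of the table. The second sets the priority: "Most importantly, the percentage of acceptable/good view (grade 3 or 4) will be compared to poor view (grade 1".

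The hypothesis is "The i-gel LMA will provide a better bronchoscopic view of the glottic aperture than the Air-Q LMA", and the aim in the background section is that "we will determine which device provides a clearer passage to the glottic opening". Nowhere is grade 2 called good, intermediate or poor, and no denominator is given for the percentage. No other primary endpoint is named, so the second sentence is the nearest thing to one.

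**The concern.** A table of grades 3-4 against grade 1 has no cell for grade 2. Its percentage is the probability of a good view given that the grade is not 2. Grade is observed after randomisation and is what the device is expected to change, so the two arms can lose different numbers of patients for reasons tied to the outcome.

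Two things can then go wrong. A true difference in the good-view rate can be hidden. Or a difference can appear under the label of good view when the good-view rates are equal and only the split between grades 1 and 2 differs. The second is a real difference in view with the wrong name, not a false positive.

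Because the denominator is not fixed in advance, either version could also be chosen after the data are seen.

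**Working it through.** **Inputs.** From the protocol: four grades, 100 patients, two devices, Fisher's exact test. Assumed, because the documents do not give them: 50 per arm, two-sided 0.05, and every grade distribution below. The sample size of 100 has no stated rates, power or effect size behind it, so there is no planned figure to reproduce.

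**What each version estimates.** Let P1 to P4 be the grade probabilities in an arm.

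- Grade 2 dropped: (P3+P4) / (P1+P3+P4).
- All randomised patients: P3+P4.

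Since P1+P3+P4 = 1-P2, the two agree only when P2 = 0.

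**Worked table (hypothetical counts).**

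| | Grade 1 | Grade 2 | Grade 3 | Grade 4 |
|---|---|---|---|---|
| i-gel | 5 | 25 | 10 | 10 |
| Air-Q | 10 | 5 | 15 | 20 |

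- Grade 2 dropped: i-gel 20/(20+5) = 20/25 = 80.0%; Air-Q 35/(35+10) = 35/45 = 77.8%. Difference +2.2 points, Newcombe 95% CI -19.2 to +20.2, Fisher p=1.00. Patients used: 25+45 = 70 of 100.
- All patients: 20/50 = 40% versus 35/50 = 70%. Difference -30 points, 95% CI -46.5 to -10.5, p=0.0046.
- Exact test on all four grades: p=0.00016.

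The direction of the point estimate reverses. The four-grade test would still show that the distributions differ.

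**Rejection rates** (simulation, 20,000 trials per row, 50 per arm, Fisher two-sided 0.05). Percentages are grades 1/2/3/4 where all four are given.

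| Scenario | Grade 2 dropped | 3-4 vs 1-2, all patients | Mean number left when grade 2 is dropped |
|---|---|---|---|
| (a) Worked-table proportions as true rates | 3.6% | 83.1% | 70 |
| (b) Good view 50% in both arms; grade 1/grade 2 = 5/45% vs 25/25% | 59.9% | 3.5% | 65 |
| (c) Identical arms, 20/20/30/30% | 3.6% | 3.3% | 80 |
| (d) Odds ratio 3, Air-Q 5/30/30/35% | 10.8% | 55.5% | 78 |
| (d) Odds ratio 3, Air-Q 15/25/30/30% | 39.2% | 60.4% | 81 |
| (d) Odds ratio 3, Air-Q 30/10/30/30% | 58.7% | 60.6% | 92 |
| (d) Odds ratio 3, Air-Q 30/5/30/35% | 55.5% | 55.8% | 96 |

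In (b), grade 1 versus grades 2-4 in all patients rejects 74.9% of the time, because the grade 1 difference is real. Row (c) shows no type I inflation. Across the rows of (d), the power lost by dropping grade 2 runs from 55.5-10.8 = 44.7 points to 55.8-55.5 = 0.3 points.

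**The case against.** The strongest reply is that the sentence never says grade 2 patients are excluded and never names a two-by-two table. It could mean the percentage of good views and the percentage of poor views in each arm, side by side, over all patients. That reading is possible, and conditioning on outcome is then an inference. But the text does not state it, and under it grade 2 still has no category and the top-ranked test is still undefined.

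The general sentence about Fisher's test may also cover all four grades. If so, grade 2 is tested and every cell is visible. With a four-grade chi-square test as a stand-in, rejection is about 99% in (a), 78% in (b) and 67 to 68% in (d), higher than for grades 3-4 versus 1-2. This stands: grade 2 is not necessarily lost from every analysis. An unordered test does not say which device gives more good views, however. The tabulated counts would show it, but the plan ranks the other comparison first.

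The sizes do rest on assumed rates, and (a) is an unfavourable example: i-gel has both fewer poor and fewer good views. With grade 2 uncommon, the loss is close to nil.

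Finally, calling grade 2 not good is a classification, and the cords are seen in that grade. Grade 1 versus 2-4 is also defensible; on the worked table it gives 5/50 versus 10/50, p=0.26. That is a reason to report it too and to choose the primary split in advance.

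**Conclusion.** The concern holds and should be settled before any outcome data are examined. It is certain from the text that grade 2 has no category and that no denominator is given. That the analysis conditions on outcome follows from the plain reading; the softer readings leave the leading test unspecified.

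The consequence ranges from negligible to a change in the size, significance and direction of the headline result. Which applies depends on how common grade 2 is and whether the devices differ in it, and the documents give no figure for either. Confidence in the practical size is therefore moderate. The fault is in what is estimated and in lost power, not in the false-positive rate when the arms are identical.

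**What to change.** Replace the second sentence of the analysis section with: *The primary comparison is the proportion of all randomised patients in each device group with an acceptable/good view (grade 3 or 4) versus not (grade 1 or 2), by Fisher's exact test, with the difference in proportions and its 95% CI.*

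Add that grade 1 versus grades 2-4 and the full four-grade table are secondary comparisons, also in all randomised patients. If the investigators prefer an ordinal comparison of the four grades as primary, that also keeps every patient, provided it is named in advance.

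The cost is one or two sentences, with no new patients, data or procedures. The small downside is that grade 2, in which the cords are visible, counts as not good in the primary comparison; the secondary comparisons make that visible.
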